An independent Clinical Endpoint Committee (CEC) will review all cases of relapses and adjudicate each to see if it meets the protocol-defined relapse in the double-blind period. In order to ensure that no relapse events are missed by the Investigator, the adjudication process will include a concurrent review of all cases to determine if a possible relapse event has been missed.

In summary, treatment with satralizumab is an approach for a specific therapeutic strategy in NMO with possible advantages for patients. All necessary measures are taken to closely monitor the safety of the treatment and thus to protect the patients enrolled in this study. The possible benefits are deemed to outweigh the potential risks involved in participation in this study.

The Clinical Development Program of satralizumab in NMOSD currently consists of two ongoing pivotal placebo-controlled randomized, double-blind Phase 3 studies. The double-blind periods of both studies have been completed (please refer to the latest Investigator's Brochure for a summary of the study results), and the studies are currently ongoing in their open-label extension (OLE) periods.

A multicenter, open-label, uncontrolled study to evaluate the pharmacokinetics, safety, tolerability, and pharmacodynamic effects of satralizumab in children from 2 to less than 12 years of age is planned to start in Q4 2020.

The first study described here (Study BN40900, also known as Study SA-309JG, the monotherapy study) is a multicenter, randomized, double-blind, placebo-controlled, Phase 3 study of satralizumab monotherapy for treatment of NMOSD that was recommended by FDA at the meeting of 11 July 2013.

In addition, the Sponsor *is conducting* a second study (Study BN40898, also known as Study SA-307JG, the add-on study), a multicenter, randomized, double-blind, placebo-controlled, Phase 3 study of satralizumab as an add-on to widely used baseline immunosuppressive therapies (ISTs) for the treatment of NMOSD.

To date, a Phase 1 single ascending dose study in healthy subjects (SA-001JP), and a Phase 1 multiple dose study in patients with rheumatoid arthritis (SA-105JP) have been conducted.

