3.3.1.2 Secondary Endpoints

- Change in VAS score for pain
- Change in FACIT fatigue score
- Change SF-36 score
- Change in EQ-5D score
- Change in T25W score
- The proportion of relapse-free patients
- ARR
- Change in mRS score
- Change in ZBI score
- Change in EDSS score
- Change in visual acuity (Snellen chart)
- Change in low-contrast visual acuity (by LCSLC)

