Visual acuity will be measured by a Snellen 20-foot wall chart. The test will be performed monocularly and patients may use their habitual distance glasses or contact lenses.

The same visual acuity testing method is to be employed for all study visits for each patient.

Change in low-contrast visual acuity (Low-contrast Sloan letter chart (LCSLC))

The LCSLC is the testing to evaluate the visual function and captures the minimum size at which individuals can perceive letters of a particular contrast level. The change in binocular visual acuity, as assessed by the number of letters read correctly from 2 meters distance on 100% (high contrast, used to measure visual acuity as a descriptor of the study cohorts), 2.5% and 1.25% contrast level Sloan letter charts, will be analyzed from baseline to every 24 weeks after the baseline visit.

A mixed-effects model repeated measures (MMRM) analysis will be used for the change from baseline in EDSS, SF-36, VAS for pain, FACIT fatigue, T25W, mRS, ZBI and EQ-5D scores, as well as visual function testing (including visual acuity tests of Snellen and low-contrast Sloan letter chart). The model will include treatment group, protocol-specified visit, treatment-by-visit interaction as fixed effects; the baseline measurements as a covariate; and visit as a repeated measure. *An* unstructured covariance matrix will be assumed in the model.

If the unstructured covariance matrix does not converge, other covariance structure will be used. If treatment-by-visit interaction is not statistically significant, we still keep the full model.

If the normality assumption for the secondary efficacy variable does not hold, a generalized estimating equation or Generalized Linear Mixed-effect model analysis will be used. The assessment will be performed prior to un-blinding and details will be mentioned in the SAP.

Use of rescue medication

The use of rescue medication is based on treated clinical relapses. If a patient has at least one treated clinical relapse, then this patient is counted as a patient with rescue medication use. The use of rescue medication will be analyzed with a logistic regression model with treatment group, prior therapy for prevention of NMO/NMOSD attack (B-cell depleting therapy or immunosuppressants/others), and the type of the

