most recent attack in the last year prior to screening (first attack or relapse) as covariates. The odds ratio, corresponding 95% CI, and p-value for the treatment group will be reported. This analysis is conducted for the double-blind period.

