- A figure of Kaplan-Meier estimate of TFR (protocol-defined relapse) will be presented by treatment group.
- Analysis of TFR (protocol-defined relapse) will be performed using stratified log-rank test.
- Analysis of TFR (protocol-defined relapse) will be performed using stratified Cox regression.

TFR (protocol-defined relapse) will be presented for the subgroups defined in section 4.10.1.5.

Additionally, sensitivity analyses of TFR (protocol-defined relapse) using a weighted stratified log-rank test, TFR (clinical relapse), TFR (treated clinical relapse), TFR (treated clinical relapse: optic neuritis), and protocol-defined relapse based on CEC adjudication (regardless of assessment limit of 7 days) will be conducted for ITT as follows For all sensitivity analyses, the same strata as for the primary endpoint will be used.

TFR (protocol-defined relapse) using a weighted stratified log-rank test: The sample size assumptions include a delayed treatment effect (see section 4.14). The influence of a

TP-GDO-WW-016-01 Confidential Version 7.0
Effective Date: 28Aug13 Version Date: 28NOV2018
Related to: SOP-GDO-WW-019 Page 22 of 60

potential delayed treatment effect will be assessed by using a weighted log-rank test using Fleming-Harrington weight function. Treatment effect is estimated adjusting for a change in the hazard ratio over time (i.e. non-proportional hazards). Based on simulations using blinded SA309 data, the parameters of the weight function are set to be rho=0 and gamma=1 (Lee 2007).

Clinical relapses: All relapses reported by investigators will be handled as events for TFR

Treated clinical relapses: Relapses treated with rescue therapy will be handled as events

Treated clinical relapse: optic neuritis: Relapses treated with rescue therapy and judged as optic neuritis by the investigator will be handled as events.

Optic neuritis will be identified via relapse assessment form before data base lock (for details see appendix 7.3). The same censoring rules as for the primary endpoint will be applied, except for the specific event of interest.

TFR (protocol-defined relapse) censored by affecting medications: Censored at the first timing of the start date of following medications:

- 1. Relapse prevention therapy
- 2. Rescue therapy
- 3. Systemic administration of steroid for other indication for more than 5 days
- A summary table of Kaplan-Meier estimate of TFR (clinical relapse) will be presented by treatment arm.

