5.5 Amendment from Ver 5.0 to 6.0

The primary purpose of this SAP amendment is to follow the FDA comments:

FDA Response dated 28th March 2017 for type C meeting Question 7:

We agree that an asymptotic log-rank test instead of a permutation based log-rank test can be used as the primary analysis method. You may keep the permutation based logrank test as a secondary analysis method.

Another purpose is to revise the context to align with the amended protocol version 7.0 dated 13th July 2017. The following changes are made in this Statistical Analysis Plan (SAP) from the previous version of SAP due to the amendment to the protocol.

For primary endpoint, analysis method has changed to stratified log-rank test from the log-rank based permutation test.

TP-GDO-WW-016-01 Confidential Version 7.0 Effective Date: 28Aug13 Version Date: 28NOV2018 Related to: SOP-GDO-WW-019

- Only treatment-emergent adverse events are collected in this study. Previously the SAP contained summaries of adverse events and treatment-emergent adverse events, the latter were removed to avoid redundancy.
- Detailed description on the identification of the following adverse event were added: serious infections, opportunistic infections, anaphylaxis, injection related reactions and injection site reactions.
- Detailed description of the following efficacy evaluation is added: EQ-5D Scoring and Visual acuity function.
- Detailed description of the immunogenicity and immunogenicity analyses were added.
- The analysis of relapse-free subjects using logistic regression will not be conducted because of a lot of early events.
- Clarify the definition of baseline ARR.
- Resolve inconsistencies mainly for scope of analysis in SAP.

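### The double-blind logistic regression of rescue-medication use in Protocol 6.5.2 is in no endpoint list and not in SAP 7.0; the SAP's planned time-to-event analysis of the same event should carry the result.

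*Protocol*

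**What the plan says.** Protocol Section 6.5.2 closes its account of the secondary endpoints with a paragraph on rescue medication. The outcome is binary: "If a patient has at least one treated clinical relapse, then this patient is counted as a patient with rescue medication use". On the model it says "The use of rescue medication will be analyzed with a logistic regression model"; the covariates are treatment group and the two stratification factors, and no exposure or follow-up term is named. On output and period: "The odds ratio, corresponding 95% CI, and p-value for the treatment group will be reported. This analysis is conducted for the double-blind period".

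The variable is not among the twelve secondary endpoints in the Synopsis, Section 2.1 or Section 3.3.1.2 (that list ends at "Change in low-contrast visual acuity (by LCSLC"), nor among the efficacy variables in SAP 3.2.1.

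SAP 7.0, aligned to Protocol 8.2AB, handles rescue treatment in three other ways:
- drug tables (4.8);
- a time-to-event sensitivity analysis of the primary endpoint (4.10.2), where "Treated clinical relapses: Relapses treated with rescue therapy will be handled as events", with Kaplan-Meier estimates, a stratified log-rank test and stratified Cox regression;
- an annualized rate table for treated clinical relapse (4.10.3.2).

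Version 10 states that "The double-blind periods of both studies have been completed" (Section 1.3), cites double-blind findings in Section 5.1.1, and attributes its Section 6 update to extension-period efficacy analyses.

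**The concern.** There are two separate problems.

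The first is status. A comparison with its own odds ratio and p-value sits under the secondary-endpoint heading, in a protocol version written with double-blind results available, and has no counterpart in the supplied SAP. A report reader could take it for a pre-specified secondary endpoint. The amendment rationale would not correct that, because it mentions extension analyses only, whereas this analysis covers only the double-blind period.

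The second is the estimate. Entry is staggered, and each patient's double-blind period ends on a different day (SAP 4.2). A patient who leaves after a few weeks without a treated relapse counts the same as one observed relapse-free for two years. The event is also common under the design assumptions, so an odds ratio lies well away from the risk ratio. A reader who takes one minus the odds ratio as the risk reduction would overstate the benefit considerably.

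**Working it through.** **Status: the documents side by side**

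| Place | Rescue-medication use |
|---|---|
| Protocol Synopsis, 2.1, 3.3.1.2 | Not listed |
| SAP 3.2.1 | Not listed |
| SAP 4.10.3 | No logistic model |
| SAP 4.10.2 | Treated clinical relapse: Kaplan-Meier, stratified log-rank, stratified Cox |
| Protocol 6.5.3.1 | Treated clinical relapse listed as a sensitivity version of the primary endpoint |
| Protocol 6.5.2 | Logistic regression, odds ratio, p-value, double-blind period |
| Protocol 6.5.2, SAP 4.10.1.4 (fixed sequence) | Covers time to first relapse, VAS pain and FACIT fatigue only |

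The outcome therefore had a planned analysis. What lacks one is the binary model and its odds ratio. Time to EDSS worsening in the double-blind period (Protocol 6.5.2) is likewise absent from SAP 7.0, which gives only a summary table and MMRM for EDSS.

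**Timing.** SAP 7.0 is dated 28 November 2018. Protocol 3.1.3 says the data monitoring committee was disbanded in December 2018, after the double-blind periods had ended. Version 10 is later still.

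**Inputs for the size** (Protocol 6.2, SAP 4.14): 90 patients, 2:1 (60 and 30); placebo hazard 1.1295 per year; hazard ratio 1.0 for 2 months, then 0.25; 10% dropout over 2 years, i.e. −ln(0.9)/2 = 0.0527 per year; 33 months of accrual; 44 events.

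**Reproducing the plan's own figures**
- Mean rate: 0.7 × 1.5 + 0.3 × 1.0 = 1.35.
- Gamma-Poisson with variance/mean √2: k = 1.35/(√2 − 1) = 3.259, and P(0) = (1/√2)^3.259 = 0.323, matching 32.3%.
- Hazard: −ln(0.3232) = 1.1295, matching.
- Simulated two-sided log-rank power at 44 events is 82% (linearly increasing accrual) to 83–84% (uniform), consistent with at least 80%.

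**Odds ratio and risk ratio at about 44 events.** The documents give no rate for treated clinical relapse, so the planning hazard for the primary endpoint stands in, with every relapse taken as treated. OR = [p_s/(1 − p_s)]/[p_p/(1 − p_p)] and RR = p_s/p_p, where p_s and p_p are the probabilities of an observed event on satralizumab and placebo.
- Uniform accrual, 33.4 months: p_p = 0.685, p_s = 0.389. Events: 30 × 0.685 + 60 × 0.389 = 43.9. OR = (0.389/0.611)/(0.685/0.315) = 0.29. RR = 0.389/0.685 = 0.57.
- Increasing accrual, 38 months: p_p = 0.702, p_s = 0.384. Events: 30 × 0.702 + 60 × 0.384 = 44.1. OR = (0.384/0.616)/(0.702/0.298) = 0.26. RR = 0.384/0.702 = 0.55.

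Under uniform accrual, an odds ratio read as a 71% reduction would stand for a 43% lower proportion with an event.

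**Type I error.** In simulations with no treatment effect, a crude unadjusted test of the odds ratio rejected in 2.6–4.3% of trials across the cut-offs examined. Omitting follow-up does not inflate false positives.

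**Efficiency.** With the planned effect and stopping at 44 events (uniform accrual), the crude odds-ratio test rejected in 75% of simulated trials, against 83% for the log-rank test.

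**The case against.** The strongest reply is that this is largely labelling. The outcome was pre-specified as a sensitivity version of the primary endpoint, and the preferred time-to-event analysis is already in both documents. The fixed sequence excludes rescue medication, so no document calls this p-value confirmatory. The protocol says openly that an odds ratio will be reported. The null test is not invalidated. All of this stands, and it keeps the point modest. It does not explain why a model absent from SAP 7.0 appears under secondary endpoints without being marked as such.

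Four stronger readings are tempting, and the documents do not support them.
- **The analysis is proved post hoc.** Protocol 8.2AB, to which SAP 7.0 is aligned, and Version 9 were not supplied, so the paragraph's date of entry cannot be shown.
- **The odds ratio will drift with the cut-off.** The double-blind period closes at 44 relapses or 1.5 years after the last randomization, whichever comes first, and it is already over. There is one fixed data set; later cut-offs at the planning hazards imply more events than the rule allows.
- **The SAP had already rejected this model.** Its amendment log says "The analysis of relapse-free subjects using logistic regression will not be conducted because of a lot of early events". That entry concerns a different variable, and its stated reason is not missing follow-up time.
- **Selection among many endpoints inflates the false-positive rate by a known amount.** The number of candidates would have to be invented, and this outcome overlaps the primary endpoint, so it is not an independent null.

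**Conclusion.** The point holds as one of status and method. Rescue-medication use is in no endpoint list and has no logistic analysis in SAP 7.0. Its late addition to the protocol is strongly suggested but not established. The model discards follow-up time although a planned stratified log-rank and Cox analysis of the same event exists.

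The consequence is an odds ratio of about 0.26–0.29 beside a risk ratio of about 0.55–0.57, at the planning hazards and about 44 events. This rests on every relapse being treated and on the primary-endpoint hazard standing in for the treated-relapse hazard; the real figures will differ.

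Primary and key secondary conclusions are untouched. The follow-up and odds-ratio criticisms do not apply to the time-to-EDSS-worsening analysis, which is a Cox and log-rank analysis; for that one the only issue is its absence from SAP 7.0. The time-to-event replacement is not perfect either, because with the assumed 2-month lag an average Cox hazard ratio still depends somewhat on follow-up.

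**What to change.** In Protocol 6.5.2 and the study report:

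1. Make the SAP 4.10.2 analysis of time to first treated clinical relapse (stratified log-rank, stratified Cox, Kaplan-Meier proportions by arm) the rescue-medication result for the double-blind period.
2. If the logistic analysis is kept, label it as not in SAP 7.0, exploratory and outside the fixed testing sequence, and mark its p-value as nominal. Give the proportions with an event beside the odds ratio.
3. Separately, give the double-blind time-to-EDSS-worsening analysis the same label.
4. State in the report when each of these two analyses was added, citing the protocol version.

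The cost is wording only, since the replacement analysis is already planned. The one thing given up is presenting rescue-medication use as a stand-alone secondary endpoint.

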6.5.3 Further Analysis

6.5.3.1 Sensitivity Analysis for Primary Endpoint

Several sensitivity analyses are planned for the primary efficacy analysis of TFR to account for the potential impact of differences in definition of primary endpoint. In this analysis TFR will be defined as follows:

- Clinical Relapse.
- Treated Clinical Relapse.
- Treated Clinical Relapse: Optic Neuritis.
- Protocol-defined relapse based on CEC adjudication (regardless of assessment limit of seven days).

Further details will be mentioned in the SAP.

6.5.3.2 Sensitivity Analysis for Key Secondary Endpoint

Several sensitivity analyses are planned for the key secondary efficacy analysis of VAS for pain and FACIT fatigue to account for the potential impact of differences in handling of missing data. In this analysis the following analyses will be conducted:

- The change in VAS for pain score from baseline to Week 24 in the double-blind period will be analyzed by ANCOVA method with hot-deck imputation
- The change in FACIT fatigue scale score from baseline to Week 24 in the double-blind period will be analyzed by ANCOVA method with hot-deck imputation

Further details will be mentioned in the SAP.

6.5.3.3 Subgroup Analysis

The subgroup summary tables will be presented by AQP4 antibody status at screening (positive/negative) in NMO and NMO/NMOSD. In case that satralizumab does not show the effectiveness in NMO patients who are AQP4 antibody negative at all, companion diagnostics co-development will be considered by using this data. Further details will be mentioned in the SAP.

6.6 SAFETY ANALYSES

All safety analyses will be performed on the SAF. Safety variables to be assessed are AEs, AESIs, SAEs, IRRs, injection site reactions, patient withdrawals due to AEs, change in 12-lead ECGs, measurements of laboratory parameters, and vital signs (including body weight).

Summary tables for number and percentage of patients with adverse drug reactions which AEs related to study treatment will be tabulated.

Adverse events will be summarized by SOC and preferred term based on Medical Dictionary for Regulatory Activities (MedDRA) coding, and grade of severity. In addition, the incidence of AEs leading to withdrawal from treatment and SAEs will be tabulated.

Laboratory values (including hematology, blood chemistry, and urinalysis), frequencies of laboratory abnormalities, vital signs (temperature, SBP, DBP and pulse rate), physical examination 12-lead ECG, and suicidality (C-SSRS) will be summarized. Measurement and change from Baseline in continuous laboratory parameters (hematology, clinical chemistry, and urinalysis), continuous ECG, vital signs (blood pressures and pulse rate), and body weight will be summarized using descriptive statistics. When analyzing categorical data, the number and percentage of patients in each category will be presented. In addition, shift tables may be used to evaluate the number and percentage of patients having a different post-baseline status when compared to their baseline status. Numbers of patients who meet the marked abnormality criteria will also be presented.

6.7 PHARMACOKINETIC/PHARMACODYNAMICS ANALYSES

Descriptive statistics, such as geometric mean, geometric coefficient of variance (CV) and the 95% CI for the geometric mean for the serum satralizumab concentration, as well as arithmetic mean, SD, median, minimum, and maximum on the measured serum satralizumab concentration, IL-6, sIL-6R, anti-AQP4 antibodies, and plasmablasts will be calculated by visit and per defined time window post-dose for the PK-PPS.

An exploratory analysis to identify any potential relationship among serum satralizumab concentration and pharmacodynamics (CRP, IL-6, sIL-6R, plasmablasts and anti-AQP4 antibodies) will be performed. These results will be described and reported in the clinical study report.

In addition, nonlinear mixed-effects modeling will be used to analyze the sparse sampling dose-concentration-time data of satralizumab. The data from this study will be pooled with data from SA-001JP study, SA-105JP study and BN40898 (SA-307JG) study to develop a population PK model for satralizumab. A covariate analysis will be conducted to evaluate the effect of covariates on satralizumab exposure. Some covariates such as body weight, age and gender will be included in the covariate analysis. Population and individual estimates of primary PK parameters [e.g., clearance (CL/F), distribution volume (V/F)] and secondary PK parameters [e.g., area under the serum concentration-time curve (AUC), average trough serum concentration (C_{trough})] will

be computed and used to explore exposure response relationship on primary and key secondary as well as PD marker and safety.

Details of this mixed-effects modeling analysis, exploration of exposure-response and the results will be described and reported in a document separated from the clinical study report.

6.8 IMMUNOGENICITY

The percentage of patients who have positive or negative antibody results will be tabulated. PK/PD, efficacy parameter and safety will be summarized by anti-drug antibody status.

6.9 HANDLING MISSING DATA

For TFR, patients who have not relapsed at the time of analysis, the TFR will be censored on the date of end of the double-blind period (see the section “Length of Study” in PROTOCOL SYNOPSIS). Further details will be mentioned in the SAP.

For key secondary endpoints, missing data at Week 24 in the double-blind period will be imputed by a BOCF and for the purpose to assess the robustness of the imputation method, we will also conduct hot-deck imputation as sensitivity analysis.

For secondary continuous endpoints, a MMRM analysis incorporating data in double-blind phase will be used to utilize data collected over time with consideration of the variance-covariance matrix of the repeated measures. This method allows a general unstructured variance-covariance matrix and will include data from patients with incomplete data from some scheduled time points.

For the FACIT fatigue questionnaire, if there are less than 7 responses recorded, then the total fatigue score will be considered missing. If there are 7 or more responses recorded, then the total fatigue score for that questionnaire will be calculated as the average of the non-missing scores multiplied by 13.

Detailed methods for handling of missing data will be mentioned in the SAP.

